**Table 1 Titration Procedure**

Electrode Placement/Age	Threshold % Energy	Dose at Subsequent ECT Treatment	
		% Energy (Bilateral)	
Bifrontal - Under 50	5		10

	10	15
	20	30
	40	60
	80	100
Bifrontal - 50 years and older	10	15
	20	30
	40	60
	80	100
	100	100

## 7. Assessment Instruments and Procedures

### a. Raters

All assessments will be performed by trained raters. Raters will be masked to the anesthetic agent used in ECT procedure. For safety purposes the anesthesiologist and the treating psychiatrist will not be masked to the anesthetic agent used. Raters will not be physically present in the treatment room during the procedure.

### b. Assessment Instruments

The primary outcome measure is the HRSD-24 which will be administered at baseline and before each treatment. The HRSD-24 is a semistructured interview designed to rate the severity of depressive symptoms in patients with a primary depressive illness. We will use the 24-item version, which includes three items in addition to the original 21 (i.e., Helplessness, hopelessness, worthlessness).

Brief Psychiatric Rating Scale (BPRS) (Hillside Anchored version) BPRS will be administered at screening and after last ECT treatment.

Psychotic symptoms will be measured by the four item positive symptoms subscale (consisting of suspiciousness, hallucinations, unusual thought content, and conceptual disorganization) of the Brief Psychiatric Rating Scale (BPRS). After each ECT treatment BPRS+ will be administered as following: after full orientation recovery, two hours post ECT. If any of the items are positive (2 or higher) BPRS+ will be re administered at 4 hours post ECT. If symptoms persist, patients will be further evaluated by a study psychiatrist and will be treated clinically as needed. Of note, that as part of standard care, patients are under constant observation and monitoring after ECT until they are deemed stable to be discharged from the unit.

**Clinician-Administered Rating Scale for Mania (CARS-M):** The CARS-m is a brief, clinician-administered, semistructured interview, which rates presence versus absence of a symptom, its severity, and symptom change in response to treatment. It is used to characterize manic behavior, but also to capture psychotic symptoms. These items yield two subscale scores one for mania (items 1-100 and one for psychosis (items 11-15).

The secondary outcome measures are the scores of neuropsychological (NP) battery. The neuropsychological (NP) battery is administered to all subjects at baseline (prior to the first ECT), on ECT #4 and following the end of the acute phase of ECT. In addition the MMSE will be performed prior to each ECT session and assessment of postictal recovery of orientation after each ECT session.

The neuropsychological test battery consists of the following instruments:

- Reading subtest of the Wide Range Achievement Test, 3rd Edition (WRAT-3), which will only be administered at baseline
- Mini- Mental State Examination (MMSE)
- Postictal Recovery of Orientation
- Rey Auditory Verbal Learning Test (RAVLT)-Immediate
- Autobiographical Memory Interview – Short Form (AMI – SF)
- Subjective Memory Questionnaire (SMQ)
- The Stroop Color Word Test (SCWT) (Golden version)
- Trail Making Test Part A & B
- WAIS-III Digit Symbol
- Wechsler Adult Intelligence Test-Third Edition (WAIS-III), Digit Span Subtest
- Controlled Oral Word Association Test (COWAT)
- N-Back

The cognitive domains to be assessed include orientation/global functioning, verbal anterograde memory, autobiographical (retrograde) memory, and subjective memory.

**Global Functioning:** The Reading subtest of the Wide Range Achievement Test, Third Edition (WRAT-3) will be administered at baseline to provide an estimate of premorbid intellectual functioning. The reading score in particular has shown a moderate correlation with WAIS Full Scale IQ scores and provides a sufficient estimate of average IQ levels. This has also been found to be true among individuals exhibiting cognitive decline. The Mini-Mental State Exam (MMSE) is a measure of global cognitive functioning with a maximum score of 30. Reliability and validity have been well established and alternate forms are available.

**Orientation** Postictal recovery of orientation will be assessed following every ECT treatment utilizing the Sabin method. According to this method, once the patient gains spontaneous respiration, orientation will be continually assessed (in 15-minute intervals) by asking the patient

to state his/her name, age, date of birth, day of the week, and current location. The assessment will continue until the patient correctly answers all five questions or until a time limit of 90 minutes is reached.

**Memory:** One of the most sensitive formats of assessing anterograde verbal memory is word list learning, given its relative freedom of associative context. The Rey Auditory Verbal Learning Test (RAVLT) is brief and easy to administer and has been well-validated. Equivalent alternate forms are available.

Retrograde amnesia for autobiographical information will be assessed by the Autobiographical Memory Interview (AMI), which was originally developed by Weiner, Squire, and colleagues, and later expanded by Sackheim et al.

The Subjective Memory Questionnaire (SMQ) will be used as a self-report measure of memory functioning. Most questions on this measure require an evaluation of memory or learning for specific material and cover a suitable range of everyday memory activities.

Wechsler Adult Intelligence Test-Third Edition (WAIS-III), Digit Span Subtest - The WAIS-III Digit Span subtest assesses immediate span of auditory attention as well as working memory. In this task subjects are required to repeat sequences of verbally presented digits forward and backward.

WAIS-III, Digit Symbol Subtest - The WAIS-III Digit Symbol subtest task measures both visual scanning and graphomotor speed. This subtest requires subjects to match meaningless symbols with the numbers 0-9 based on a key presented at the top of the form.

Trail Making Test Part A & B - The Trail Making Test (Parts A & B) is a measure of attentional resources. Part A is a simple scanning task in which the subject is required to connect randomly arrayed numbers in order, while the more demanding Part B requires subjects to sequentially alternate between numbers and letters. Score on the test is the time required to complete each sequence. Part B is primarily conceptualized as a measure of the frontal lobe "executive" functions of visual search, set-switching and conceptual flexibility.

The Stroop Color Word Test (SCWT) (Golden version) The SCWT is a commonly used task measuring selective attention and inhibitory control, or cognitive control. This test is designed to measure the ease with which a person can shift his/her perceptual set to conform to changing demands and suppress habitual response in favor of a more effortful one.

Controlled Oral Word Association Test (COWAT) (Benton & Hamsher, 1989): This is a measure of sustained verbal fluency. It requires the subject to produce as many words as possible that begin with specific letters in a 60-second period. Two matched sets of letters (CFL and PRW) are used as alternate forms of the test. The score is the sum of all correct words produced during the three 60-second trials with adjustments for age, sex, and years of education.

The  $n$ -back task requires on-line monitoring, updating, and manipulation of remembered information and is therefore assumed to place great demands on a number of key processes within working memory. It is a computerized continuous performance task. The subject is presented with a sequence of stimuli, and the task consists of indicating when the current stimulus matches the one from  $n$  steps earlier in the sequence. The load factor  $n$  can be adjusted to make the task more or less difficult.

Treatment side effects will be measured using the Treatment Emergent Side Effects Scale (TESS) This 49-item scale assesses the presence and severity of a range of potential side effects including 1) behavioral toxicity such as agitation; 2) neurological effects such as tremor; 3) cardiovascular effects such as palpitations; 4) autonomic effects such as dry mouth; and 5) other effects.

### c. Timing of Assessments

**Table 2: Timing of Assessments**

Assessment	Baseline 	3X weekly before ECT	3X Weekly following ECT	ECT # 4	After last ECT 
Informed Consent	X				
Past Psychiatric History	X				
Medical Evaluation	X				
HRSD-24	X	X			X 
BPRS	X				X
BPRS positive items		X	X 		
SCID	X				
Neuropsychological Battery	X			X 	X 
Reorientation time			X		X
MMSE		X			
TESS	X				X

 Performed within 24 hours before the first ECT;  24hrs post ECT;  24-72 hrs post last ECT;

 1 week post last ECT  BPRS+ after full recovery, at 2h, at 4h if BPRS+2h >2

### d. Outcome Criteria

## **1. Remitter criteria**

- (a)  $\geq 60\%$  decrease from baseline in HRSD total score, *and*
- (b) HRSD  $\leq 10$  on two consecutive ratings, *and*
- (c) HRSD does not change  $> 3$  points on last 2 consecutive treatments. We do not define a specific minimum or maximum number of ECT for a patient to be classified as a remitter.

## **2. Non-remitter criteria**

- (a) patient does not reach above remission criteria, *and*
- (b) has at least 10 treatments, *and*
- (c) reaches a plateau defined as no clinical improvement ( $< 3$  point decrease in HRSD after last 2 consecutive treatments).

*Drop-outs* are patients who discontinue treatment before they can be declared remitters or *non-remitters*. Premature exits in this study will be analyzed as non remitters. Criteria for *premature exits* are as follows:

## **3. Premature exits**

- (a) consent for ECT or study participation is withdrawn *before 10 ECT have been administered, or*
- (b) initial ST is 80% or higher, *or*
- (c) ECT is discontinued for clinical or other reasons *before 10 ECT have been administered, or*
- (d) more than one week separates two treatments.

## **8. Risks**

There are no additional significant risks due to the study procedures. The safety of ECT is well established. The risks of the procedure are described at the standard institutional consent form that the patients sign before treatment. Patients will be approached to sign informed consent for the study only after they have consented to ECT.

Possible but infrequent complications of ECT may include headaches, myalgia, and fractures (from the muscular contractions followed by seizures), chipped or lost teeth, spontaneous seizures and, in extremely rare conditions, death.

Methohexital is the anesthetic most commonly used in for ECT. Possible adverse events of methohexital anesthesia include hypotension, pain at the injection site nausea, emesis, muscle hyperactivity (twitching, shivering, tremors, involuntary muscle movements or convulsive like movements) excitation, headache, lethargy, restlessness, and delirium upon wakening.

Ketamine is widely used in pediatric populations and it has proven to be safe. The incidence of psychotic-like symptoms in adults although more common than in pediatric population, are usually transient, rarely lasting longer than two hours. Moreover, the psychomimetic effects of ketamine are rarely observed with ECT and even then, are successfully managed with the use of a benzodiazepine. Other possible adverse events in both anesthetic and sub-anesthetic doses include transient increases in blood pressure and pulse rates as well as ataxia, nausea, dizziness, headache and confusion.

As for every medication there is the rare possibility of an allergic reaction.

All subjects will sign informed consent for the standard ECT treatment and for the anesthetic procedure and they will sign informed consent for participating in the study.

## **MRI**

There are no special benefits anticipated from participation in these studies. The risks of f-MRI scanning are minimal. There is no ionizing radiation involved in MRI, and there have been no documented significant side effects of the magnetic fields and radio waves used on the human body to date. However, because the effects of strong magnetic fields on a fetus are not well documented at this time, pregnant women will be excluded from the study. People have been harmed in MRI machines when they did not remove metal objects from their clothes or when others left metal objects in the room. All necessary precautions will be taken to prevent inadvertent presence of metal objects in the MRI room. Some subjects, even those without known history of claustrophobia may experience discomfort or even panic attacks in the enclosed setting of the magnet. All efforts will be taken to first calm subjects down and next to decide together with the participant whether or not to continue study participation.

## **9. Adverse Event Reporting**

Side-effects will be monitored by the study physician and self reports. Treatment side effects will be measured using the Treatment Emergent Side Effects Scale (TESS). Reported adverse events will be evaluated and treated according to standard treatments procedures. In the case of a serious or intolerable adverse event subjects will be withdrawn from the study and he will be referred for treatment if necessary. Serious adverse events will be reported to IRB in no more than 24 hours after occurrence or after the ECT psychiatrist is informed.

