### **Hypothesis**

We hypothesize that patients who receive ketamine anesthesia during ECT will need fewer treatments to achieve remission. At the end of the ECT course they will display fewer cognitive side effects compared to those treated with methohexitol anesthesia.

In the imaging part of this study, the main theoretical question is whether ECT exerts its effect primarily by altering networks. Our specific hypothesis is that ECT will decrease functional connectivity in the Default Mode Network.

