### **Significance**

Every year more than 100,000 patients in the United States and approximately 1,000,000 patients in the world receive ECT. According to the CORE group the average course of acute ECT for the treatment of a major depressive episode is 8 sessions. The major limiting factor in the use of ECT is the cognitive side effects, which are cumulative in nature. If the use of ketamine were able to reduce the overall number of treatments to remission or be even minimally cognitive sparing, this will have a significant positive impact in the field. Examples of the positive effects are reducing the burden of illness on patients and their exposure to possible side effects of ECT. Also, reducing patients' length of hospitalization, and decreasing the cost of mental health care. It is for these reasons that ketamine is being reexamined as a preferred anesthetic for ECT.

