### **6. ECT Procedures**

ECT will be administered following the standard 3 times per week schedule (Monday, Wednesday, Friday) until remission is achieved (defined by an HRSD-24 score of 10 or less) or until a patient is declared a non remitter (see criteria, page 15). Subjects will be withdrawn from the study if side effects become limiting, or if either the patient or principal investigator determine that ECT should be discontinued. All patients will be treated with moderately suprathreshold stimulus doses. Threshold will be determined at the first treatment and doses will be increased at subsequent treatments as needed to insure adequacy of seizures. (see section d) The average total number of ECT per patient is expected to be approximately 8 and will not exceed 15 in any case.

Both inpatients and outpatients will be brought to the ECT treatment area in the morning on the day of treatment and an intravenous catheter will be introduced and remain in place until the treatment has been completed. Blood pressure, pulse rate, ECG, and pulse oximetry will be monitored prior to anesthetic induction and continuously during the procedure.

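### Patients with limiting, serious or intolerable side effects leave the study, with no provision for the end-of-course TESS and memory tests that the tolerability comparison needs

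*Combined protocol and SAP*

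**What the plan says.** Two sections govern exit for side effects. Section 9 (Adverse Event Reporting): "In the case of a serious or intolerable adverse event subjects will be withdrawn from the study". Section 6 (ECT Procedures): "Subjects will be withdrawn from the study if side effects become limiting". Both name the study, not only the ECT course, as what the patient leaves.

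Section 7 and Table 2 set the assessment times:

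- **Full neuropsychological battery:** at baseline, then "on ECT #4 and following the end of the acute phase of ECT". A Table 2 footnote times the last one at "1 week post last ECT".
- **TESS:** at baseline and after the last ECT only.
- **Full BPRS:** "BPRS will be administered at screening and after last ECT treatment".
- **HRSD-24:** at baseline, before every treatment, and 24 to 72 hours after the last one.
- **Every session:** MMSE before ECT; reorientation and the BPRS positive items after ECT.

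Early exits have rules for remission only. The outcome criteria in section 7d count premature exits as non-remitters, and section 13 censors dropouts in the survival analysis. For cognition (Aim 2), section 13 specifies a mixed model comparing slopes for each measure, with no missing-data rule or sensitivity analysis. No early-termination visit is described.

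**The concern.** Secondary Aim A compares cognitive side effects, and the hypothesis fixes the time point: "At the end of the ECT course they will display fewer cognitive side effects compared to those treated with methohexitol anesthesia". The Significance section states: "The major limiting factor in the use of ECT is the cognitive side effects, which are cumulative in nature". On the protocol's own account, then, patients who leave because side effects have become limiting will often be those whose cognition has suffered most. They leave before the end-of-course measurement that the hypothesis concerns.

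If one arm is less well tolerated, it loses more of its worst-affected patients and its remaining data look better than they should. This can work in either direction. The aim of the pilot is to estimate effect sizes for a larger trial, so a distorted tolerability estimate would carry forward into that design.

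**Working it through.** **1. What an early-withdrawn patient contributes, if assessment ends at withdrawal**

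| Measure | Withdrawn before ECT #4 | Withdrawn after the ECT #4 battery |
|---|---|---|
| TESS | baseline only | baseline only |
| Full BPRS | baseline only | baseline only |
| Full battery (RAVLT, AMI-SF, SMQ and others) | baseline only | baseline and ECT #4 |
| HRSD-24 | each session to exit; no closing rating | each session to exit; no closing rating |
| MMSE, reorientation, BPRS positive items | each session to exit | each session to exit |

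TESS and the tests given only in the full battery are hit hardest. The background section on cognitive effects calls retrograde amnesia the commonest cognitive side effect of ECT. The instrument for it, AMI-SF, is given only in the full battery.

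**2. The plan's own yardstick (section 13)**

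The detectable slope difference is 0.05 SD per visit. Over 8 visits, 0.05 × 8 = 0.40 SD. The plan's HRSD example agrees: 0.25 points × 8 = 2.0 points, and 2.0 / 5.0 = 0.40 SD.

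**3. How likely is at least one such withdrawal in an arm of 12?**

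No withdrawal rate is given, so the risk p is assumed. The formula is 1 − (1 − p)^12:

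- p = 5%: 46%
- p = 10%: 72%
- p = 20%: 93%

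**4. Shift in a completers' final mean**

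Let k of 12 be lost, and suppose they would have scored g SD worse than those who stay. The full-arm mean is worse than the completers' mean by (k/12) × g. Both k and g are assumptions.

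| k | g = 1 | g = 1.5 | g = 2 |
|---|---|---|---|
| 1 | 0.08 | 0.125 | 0.17 |
| 2 | 0.17 | 0.25 | 0.33 |
| 3 | 0.25 | 0.375 | 0.50 |

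Against 0.40 SD this is 21% (0.083 / 0.40) to 125% (0.50 / 0.40). The whole shift enters the between-arm difference only if the other arm loses nobody in this way. Equal losses with equal gaps would cancel.

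**5. Information for the planned slope**

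For a linear slope, a patient's information is proportional to Sxx, the sum of squared deviations of the visit times from their mean. Take the last ECT as #8, the expected average in section 6.

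- Battery at 0, 4, 8: Sxx = 16 + 0 + 16 = 32.
- Battery at 0, 4, 11 (one week is about 3 sessions): Sxx = 25 + 1 + 36 = 62.
- Baseline and ECT #4 only: Sxx = 4 + 4 = 8.
- Baseline only: Sxx = 0.

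Missing the final battery removes 24/32 = 75% or 54/62 = 87% of that patient's slope information. For the arm, with 3 of 12 lost after ECT #4, (9 × 32 + 3 × 8) / (12 × 32) = 81% remains, or (9 × 62 + 3 × 8) / (12 × 62) = 78%. The loss of precision is moderate. The main worry is that the lost patients are selected on the outcome.

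**The case against.** The strongest reply is that the loss is inferred. No sentence says that assessment ends at withdrawal. Table 2 times its final column from the last ECT, and someone who stops at ECT #6 has a last ECT, so a site could treat those visits as due. The consent pages were not available for this review and may contain follow-up terms. This stands as a caution: the loss is the natural reading of the two withdrawal sentences, not an explicit instruction. That sites could differ is itself a reason to settle the wording.

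Second, the plan collects a good deal up to exit. Three stronger inferences therefore fail:

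- *That the psychosis comparison is lost.* Section 7b measures psychotic symptoms with the BPRS positive items after every ECT, repeated at four hours if positive at two. Only the final full BPRS is at risk.
- *That the decline behind the withdrawal goes wholly unmeasured.* MMSE and reorientation are listed parts of the battery and are taken every session, so acute confusion would be captured. The gap concerns tests such as RAVLT, AMI-SF and SMQ.
- *That outcomes of adverse events go unrecorded.* Section 9 provides for monitoring by the study physician and self-report, evaluation and treatment of reported events, and prompt reporting of serious ones to the IRB. The lack of a stated rule to follow events to resolution does not show that outcomes are missed.

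Third, the planned analysis is a mixed model, which uses the baseline and ECT #4 scores of patients who leave. That usually makes its bias smaller than the completers' shift. It does not remove the bias where decline after ECT #4 was not captured on those tests, and TESS has no intermediate value at all.

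**Conclusion.** The point holds in limited form and merits a wording change. Read naturally, the withdrawal rules remove the only post-baseline TESS, the final full BPRS, the closing HRSD-24 and the one-week battery for patients with limiting, serious or intolerable side effects. Those who leave before ECT #4 have no post-baseline full battery. For Secondary Aim A this missingness is probably informative, because the protocol itself identifies cognition as what limits ECT.

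The size is unknown. The 0.08 to 0.50 SD range rests on assumed losses of 1 to 3 of 12 in one arm and an assumed gap of 1 to 2 SD. It describes a completers' mean. A reader might take it as the bias in the planned slope comparison, but the documents give no basis for that, and the slope bias would usually be smaller.

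**What to change.** Leave every criterion for stopping treatment as it is. Reword sections 6 and 9 so that a patient who meets one stops study ECT and, unless consent for follow-up is withdrawn, completes the existing final column of Table 2 timed from their own last study ECT: HRSD-24 at 24 to 72 hours, BPRS and TESS, and the cognitive battery at one week.

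In section 13, state that these data enter the Aim 2 models and the side-effect tables by randomized arm. Record the reason for stopping and any treatment given afterwards.

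The cost is protocol and consent wording plus a few visits of a kind already scheduled. Some patients will refuse, and scores obtained after stopping may reflect later treatment, which is why that treatment must be recorded. The stated sample size and power figures do not change.
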